Adolescent idiopathic scoliosis (AIS) is a condition that develops during adolescence and causes a three-dimensional deformity of the spine. This deformity can include deviations in the frontal, sagittal, and axial planes and can negatively affect individuals' physical functions and balance control mechanisms. (1). Lumbopelvic rhythm refers to the coordination of spinal and pelvic movements and is a critical factor for postural stability. Scoliosis can alter lumbopelvic rhythm by affecting pelvic and lumbar region movements (2). In individuals with AIS, changes such as decreased trunk flexion-extension movements and pelvic and hip movements during walking, overactivity of muscles in the spine and pelvis, increased energy consumption, impaired balance and gait have been observed (3,4). Abnormalities in vestibular and proprioceptive inputs have also been observed, leading to changes in balance control (5, 6). Postural control requires the integration of sensory and motor systems to maintain body balance. Changes in postural control mechanisms in individuals with scoliosis can reduce mobility. In postural control assessments, individuals with scoliosis have been found to exhibit greater deviation and acceleration reactions from the center of pressure compared to healthy individuals (7, 8). This can lead to difficulties in daily living activities, increased pain levels, and decreased quality of life (9, 10). While there are studies in the literature on muscle activation, range of motion, pelvic position, gait, and balance in individuals with AIS, no studies have been found that examine changes in lumbopelvic rhythm and their relationship with the type, localization, and severity of the curve, and the effect of lumbopelvic rhythm on postural control and quality of life in individuals with AIS. Therefore, evaluating lumbopelvic rhythm in individuals with AIS can contribute to understanding the changes in movement patterns due to scoliosis and guide clinical diagnosis and treatment approaches.

The purpose of this study is;

- To identify possible differences by comparing the lumbopelvic rhythm characteristics of individuals with AIS to those of healthy individuals.
- To investigate the effects of localization, type, and severity of curvature on lumbopelvic rhythm in individuals with AIS.
- To examine the lumbopelvic rhythm in individuals with AIS during daily living activities such as trunk flexion and extension, sitting down, standing up, and walking.
- The aim is to examine the relationship between lumbopelvic rhythm and postural control, daily living activities, and quality of life.

Hypotheses;

H1: Lumbopelvic rhythm differs in individuals with AIS compared to healthy individuals.

H2: Lumbopelvic rhythm in individuals with AIS is related to the localization, type, and severity of the curvature.

H3: In individuals with AIS, lumbopelvic rhythm is associated with postural control.

H4: In individuals with AIS, the lumbopelvic rhythm differs in terms of curvature localization, type, and severity during sitting, standing, and walking.

H5: Lumbopelvic rhythm is related to quality of life in individuals with AIS.

3. Research Materials and Methods

3.1. Location of the Research

Hacettepe University, Faculty of Physical Therapy and Rehabilitation, Movement Analysis Laboratory

3.2 . Timing of the Research

The study begins on May 15, 2025, and ends on November 15, 2026.

3.3. Characteristics of Individuals to be Included in the Study and Sample Size Calculation

The study group will consist of individuals diagnosed with AIS who apply to the Faculty of Physical Therapy and Rehabilitation at Hacettepe University. Participants in the healthy group will be selected using a snowball method from among the relatives of patients or researchers who apply to the Faculty of Physical Therapy and Rehabilitation. The number of individuals to be included in the study will be determined by a power analysis after analyzing the data of 10 individuals diagnosed with AIS and 10 healthy individuals who meet the inclusion criteria.

AIS group inclusion criteria:

Those diagnosed with AIS,
Between the ages of 10 and 18,
Having a Cobb angle greater than 10°,
Pain intensity < 3
Volunteer individuals

Exclusion Criteria:

Male gender,
Body mass index ≥ 30 ,
The presence of additional pathologies affecting the lumbopelvic region (disc herniation, spondylolisthesis, hip dysplasia, rheumatic diseases, etc.),
Chronic pain lasting longer than 3 months,
Lower extremity length difference > 2 cm
Orthopedic or neurological problems affecting the lower or upper extremities.
A history of acute injury,
History of spinal surgery,
Individuals with vestibular pathology or severe balance disorders

Control Group Inclusion Criteria:

Those who have no diagnosed or known illness,
Between the ages of 10-18
Has similar demographic characteristics to the AIS Group.
Volunteer individuals

Exclusion Criteria:

Male gender,
Body mass index ≥ 30
Individuals with acute injury or pain will be excluded from the study.

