3.6. Statistical Analysis of the Research

Descriptive statistics will be used for participants' demographic and clinical characteristics (age, gender, type of scoliosis, Cobb angle, etc.). The study results will be analyzed using the "Statistical Package for Social Sciences" (SPSS) Version 16.0 statistical program. Standard deviation, mean, minimum, and maximum values will be calculated. A 95% confidence interval will be used to evaluate the reliability of the analysis results. The normality of the distribution of variables will be examined using Kolmogorov-Smirnov/Shapiro-Wilk tests and histogram graphs. For comparisons of lumbopelvic rhythm and postural control between the scoliosis and control groups, an independent samples t-test will be used if the data show a normal distribution, and the Mann-Whitney U test will be used if the data do not show a normal distribution. Pearson correlation analyses will be performed for normally distributed data and Spearman correlation analyses for non-normally distributed data to examine the relationships between lumbopelvic rhythm, postural control, pain level, and quality of life in the AIS group. The significance level will be considered to be $p<0.05$.

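### Section 3.3 lets controls be relatives of patients or researchers, while Section 3.6 compares the groups only with tests that assume unrelated participants

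*Protocol*

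**What the plan says.** Section 3.3 of the protocol sets both recruitment routes. For the AIS group: "The study group will consist of individuals diagnosed with AIS who apply to the Faculty of Physical Therapy and Rehabilitation at Hacettepe University". The healthy controls, by contrast, are to be "selected using a snowball method from among the relatives of patients or researchers". Controls must also be female, aged 10 to 18 and free of known illness, and the only matching criterion is at group level: "Has similar demographic characteristics to the AIS Group". The section has no rule of one participant per family and no requirement that a control be unrelated to an enrolled AIS participant.

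Section 3.6 fixes the tests for lumbopelvic rhythm and postural control between the groups: "an independent samples t-test will be used if the data show a normal distribution". Where normality fails, the stated rule is that "the Mann-Whitney U test will be used if the data do not show a normal distribution". The section does not mention related participants.

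**The concern.** Both tests take every observation to be independent of every other, within a group as well as between groups. A snowball sample that starts from relatives is a route by which that assumption can fail, in two ways:

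- A control may be related to an enrolled AIS participant. If their outcomes are positively correlated, the two group means move together, the independent-samples standard error is too large, and H1 loses power.
- Controls may be related to each other. The control mean then carries less information than its head count suggests, the standard error is too small, and false positives become more frequent.

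At stake are the p-values and 95% confidence intervals for H1, the hypothesis that compares AIS with healthy participants, and for the postural-control comparison made with the same tests. The estimated difference in means is not affected by this mechanism.

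**Working it through.** **Inputs from the protocol.** The control source and the tests are as quoted above. The significance level is 0.05 (Section 3.6); sidedness is not stated, so two-sided is assumed. There is no final sample size, because it "will be determined by a power analysis after analyzing the data of 10 individuals diagnosed with AIS and 10 healthy individuals" (Section 3.3). The protocol has no figure to reproduce, and the results below are ratios that hold for any equal group size n.

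**Assumed inputs.** f is the share of controls with one enrolled AIS relative, g the share of controls in sibling pairs, and ρ the correlation between relatives on the outcome. None is in the protocol. Groups are of equal size with a common variance σ².

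**Planned test.** Its squared standard error for the difference in means is 2σ²/n.

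**(a) Case-control links.** The covariance of the two means is fρσ²/n, so the true variance is 2σ²/n − 2fρσ²/n, and

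true SE / assumed SE = √(1 − fρ), actual α = 2Φ(−1.96 / ratio).

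| f | ρ | SE ratio | Actual α |
|---|---|---|---|
| 0.10 | 0.1 | 0.995 | 0.049 |
| 0.25 | 0.3 | √0.925 = 0.962 | 0.042 |
| 0.50 | 0.3 | √0.85 = 0.922 | 0.034 |
| 1.00 | 0.5 | √0.5 = 0.707 | 0.006 |

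A simulation of the t-test (40,000 runs, 30 per group) gave 0.041, 0.034 and 0.007 for the last three rows.

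**(b) Links among controls.** With a share g in sibling pairs, the variance of the control mean is (σ²/n)(1 + gρ). The variance of the difference is (σ²/n)(2 + gρ), and the SE ratio is √(1 + gρ/2).

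- Half the controls in pairs, ρ = 0.4: gρ = 0.2, ratio √1.1 = 1.049, α = 2Φ(−1.96/1.049) = 0.062. The design effect of 1.2 applies to the control mean only. On the difference, which is what H1 tests, the standard error is about 5% too small.
- All controls in clusters of size m: ratio √[(2 + (m − 1)ρ)/2]. This runs from 1.025 (m = 2, ρ = 0.1; α = 0.056) to 1.225 (m = 3, ρ = 0.5; α = 0.110).

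**(c) Both together.** The two effects partly cancel. Suppose half the controls are in sibling pairs with ρ = 0.4 and a separate 25% each have an enrolled AIS relative with ρ = 0.3. The variance ratio is 1 + 0.1 − 0.075 = 1.025, the SE ratio is 1.012 and α is about 0.053. If the separate share is 50%, the variance ratio is 1 + 0.1 − 0.15 = 0.95, the SE ratio is 0.975 and α is about 0.044.

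**(d) Nobody related.** f = g = 0, the ratio is 1 and α is 0.05.

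**The case against.** A reader might infer that the controls are the enrolled patients' own relatives, so that the design deliberately builds family pairs and the planned standard errors are simply wrong. The text does not support that. The pool also includes relatives of researchers, and the patients mentioned are not limited to AIS patients, still less to enrolled ones. The route permits family links; it does not create them by design. For the same reason a paired test is not the general answer, since no pairs are formed.

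The case for leaving the plan alone goes further, and much of it stands:

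- A case-control pair needs two eligible girls aged 10 to 18 in one family, one with AIS and one healthy, both volunteering. High shares are therefore extreme corners, and at modest shares the error is small and conservative.
- The documents give no within-family correlation for lumbopelvic rhythm or sway, so every size above is conditional. A shared age range is no evidence of a family effect, because eligibility imposes it on everyone.
- It cannot be said that family links go unrecorded. Section 3.5 gives its questionnaire items as examples, and the form is not shown.
- A statistical analysis plan might deal with related participants.

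The last point does not remove the concern. The protocol itself names both the recruitment route and the tests, and the two do not fit if relatives enrol. What stands is that the point is minor and conditional.

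**Conclusion.** The concern holds in a limited form. Section 3.3 allows related participants and Section 3.6 fixes tests that assume there are none, so the standard error for H1 is wrong to the extent that related people enrol. Its direction depends on who is related to whom. Under moderate assumptions the true type I error lies between about 0.034 (half the controls related to an enrolled case, ρ = 0.3) and about 0.062 (half the controls in sibling pairs, ρ = 0.4), against a nominal 0.05. When both kinds of link occur, the errors partly offset. Values near 0.006 or 0.110 need every control to be related to someone, with a correlation of 0.5. The effect is probably small. It is a worthwhile improvement and not a threat to the study.

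**What to change.** Record a family identifier for every participant at enrolment, covering links to AIS participants and to other controls. Add to Section 3.6 that, if any participants share a family, the group comparison will use a linear model with a family random intercept or family-clustered standard errors, and that the non-normal branch will use a family-level permutation test or a similar cluster-aware test. If no participants are related, keep the planned t-test or Mann-Whitney U.

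The rule should be conditional. With one person per family a random intercept cannot be separated from the residual, and clustered standard errors become heteroscedasticity-robust ones, so neither model collapses exactly to the planned test. An alternative is to admit one participant per family and require controls to be unrelated to enrolled AIS participants. That keeps the planned tests but narrows the recruitment pool.

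The identifier costs one form field and a slightly more complex analysis, with recruitment unchanged. It is easiest to collect at enrolment.

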3.4. Type of Research (Place an 'X' in the relevant column)

Cross-sectional	X	
Case Studies		
Cohort Studies	Retrospectiv e	
	Prospective	
Qualitative		
Other (write in place of the cross)		

3.5 . Research Methodology

Data collection will be carried out at the Movement Analysis Laboratory of the Faculty of Physical Therapy and Rehabilitation, Hacettepe University.

Participants' demographic data such as gender, age, height, and weight, as well as age at scoliosis diagnosis, age at menarche, and treatment processes, will be collected through individual self-reporting using a structured questionnaire specifically designed for this study. The questionnaire will be explained to each participant before the research process begins, and after obtaining the necessary consent, it will be completed through face-to-face interviews. The data provided by the participants will be used only for research purposes in accordance with confidentiality principles, and data security will be ensured. All data obtained during the study process will be analyzed only by the research team.

Curve pattern information obtained from the individuals' existing anteroposterior radiographic images will be recorded along with the spinal region (cervical, thoracic, lumbar) and the measured Cobb angle degrees. Axial trunk rotations will be measured with a scoliometer and added to the form. The severity of the patients' curvature will be evaluated using the Cobb angle method, which SOSORT and SRS consider a primary outcome of treatment and accept as a standard for measuring deformity in scoliosis. Measurements will be taken using data from the patient's existing anteroposterior radiographic image. The Cobb angle is defined as the angle between a line drawn from the upper edge of the upper vertebra with the greatest curvature and a line drawn from the lower plate of the lower vertebra with the greatest curvature. This will be measured using a computer program and recorded in degrees on the form. According to the SRS classification, the curve pattern is determined by the location of the apex. The primary curve apex is between the 2nd thoracic vertebra and the 11th-12th thoracic vertebrae. Individuals with curves in the intervertebral disc space are classified as thoracic, those between the 12th thoracic vertebra and the 1st lumbar vertebra are classified as thoracolumbar, those between the 1st-2nd lumbar intervertebral disc and the 4th lumbar vertebra are classified as lumbar, and curves in both the thoracic and lumbar regions are classified as double curves (19). In our study, the curves will be named according to this classification and recorded in the form.

included in the study will be performed using an Inertial Measurement Unit (IMU). Data will be collected using Movella DOT wearable sensors (Movella Inc. , Henderson, NV, USA) at a sampling rate of 60 Hz. IMU sensors will be placed at C7, the thoracolumbar junction, the lumbosacral junction, and the lateral midpoints of both thighs, and secured to the skin with a flexible band. This placement will allow for the acquisition of lumbar and hip movements. The device will be calibrated before measurements begin for each participant . The device's zero point will be determined while participants stand upright barefoot. Participants will be asked to follow a standardized movement protocol. This protocol includes: maximum trunk flexion by leaning forward while standing, maximum trunk extension by leaning backward while standing, maximum right and left trunk rotation while standing, and right and left lateral trunk flexion while standing, as well as standing up and walking. Participants will be asked to repeat each movement 3 times, and the average of the data will be taken (11,12). The movement patterns of the lumbopelvic region will be analyzed using raw data on acceleration and angular velocity obtained from the IMU device .

Postural control will be assessed using the Bertec Balance Check Screener™ strength platform (BP5050 Bertec Co. , Columbus, OH, USA) (13). The participant will be positioned on the platform with their feet parallel to each other and the distance between their feet being half shoulder width (14). In a static stance, the participant will be asked to remain as still as possible on hard and soft surfaces with their eyes open and closed, and the amount of anterior-posterior and right-left postural sway will be determined. Participants will be asked to move forward, backward, right, and left as far as they can on a hard surface with their eyes open and their feet in the same position, without breaking contact between their feet and the platform, and the amount of displacement of the center of gravity forward,

backward, right, and left (stability limits) will be recorded in cm (15,16). Each measurement will be performed 3 times, and the 3rd measurement will be used in the analysis (17). To assess quality of life, the Scoliosis

Research Society's Health-Related Quality of Life-22 (SRS-22) questionnaire will be used. The SRS-22 questionnaire is a quality of life scale specific to scoliosis. The SRS-22 is a 22-question scale with a 5-point Likert scale, divided into five subgroups: pain, general appearance/image, spinal function, mental health, and treatment satisfaction. Each question has responses ranging from negative to positive. The most negative response is worth 1, and the most positive is worth 5. The scores from each section are added together and divided by the number of questions answered to obtain the scores for the subgroups and the total score. The lowest possible score is 1, and the highest is 5. A higher score on the scale indicates improved quality of life, while a lower score indicates a lower quality of life. This shows that it has decreased. The validity and reliability study of the Turkish version of the questionnaire, which has been shown to be valid and reliable in many languages, was carried out by Alanay et al. in 2005 (19).

Pain assessment will be performed using a visual analog scale (VAS). Participants will indicate the intensity of their pain on a scale of 0 to 10, where 0 represents no pain and 10 represents unbearable pain.

A project application will be submitted to the TÜBİTAK 1002-A Rapid Support Program for the procurement of the Movella DOT wearable sensors to be used in this study.

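### Rotation, lateral flexion and lateral stability limits are taken by body side with no link to the side of the curve, so a side-specific AIS effect can be diluted

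*Protocol*

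**What the plan says.** Section 3.5 lists eight movements for the inertial sensors. Four are named by body side: "maximum right and left trunk rotation while standing, and right and left lateral trunk flexion while standing". The other four (flexion, extension, standing up, walking) are not. On the force platform, displacement forward, "backward, right, and left (stability limits) will be recorded in cm", so right and left are separate values. Static sway is different: "the amount of anterior-posterior and right-left postural sway will be determined", which is one amount per axis.

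The curve data are also set out in section 3.5. Curve pattern information "will be recorded along with the spinal region (cervical, thoracic, lumbar) and the measured Cobb angle degrees". Under the classification used, "the curve pattern is determined by the location of the apex", which gives a level and not a direction. For the scoliometer: "Axial trunk rotations will be measured with a scoliometer and added to the form"; the side of the reading is not mentioned. Curves in both the thoracic and lumbar regions form a double-curve class.

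Section 3.3 sets a criterion on curve size ("Having a Cobb angle greater than 10" degrees) and none on curve side. Section 3.6 begins its test rule with "For comparisons of lumbopelvic rhythm and postural control between the scoliosis and control groups" and names a t-test or Mann-Whitney U test, then Pearson or Spearman correlations within the AIS group. It does not say how right and left values enter either analysis.

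**The concern.** In a girl whose curve is convex to the right, bending or turning right is movement toward the convexity. In a girl whose curve is convex to the left, the same movement is away from it. Eligibility admits both, and an apex-level class can contain both. If scoliosis affects the two directions differently, a column headed right mixes two different quantities. The mean difference from controls shrinks and the spread in the AIS group grows. The same mixing would weaken a correlation between such a value and postural control, pain or quality of life.

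At stake is a real, curve-related difference in rotation, lateral flexion or lateral stability limits being reported as no difference (H1) or as a weak association (H3, H5). The variable that would prevent this can be read from a radiograph already in use, but it is not among the listed items.

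**Working it through.** The protocol states no effect size, power or final sample size (section 3.3 leaves the number to a power analysis after 10 + 10 participants), so there is no figure to reproduce. What follows is an illustration.

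**Inputs**
- From the protocol: two independent groups; significance level 0.05 (section 3.6), taken as two-sided.
- Assumed: side-specific effect d = 0.8 with within-group SD 1; equal groups sized for 80% power when values are aligned to the curve; a share p of AIS curves convex to the right, from 0.5 to 1.0.

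**Step 1, aligned values.** n per group = 2 × (1.96 + 0.8416)² / 0.8² = 2 × 7.849 / 0.64 = 24.5, so 25. Power ≈ Φ(√(25/2) × 0.8 − 1.96) = Φ(0.868) = 80.7%.

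**Step 2, right-side values without alignment.**
- Model A, opposite shifts (convex side −d, concave side +d): size of the mean shift d(2p − 1); added AIS variance 4d²p(1 − p).
- Model B, convex side only (−d, concave side 0): size of the mean shift dp; added AIS variance d²p(1 − p).
- Pooled SD = √((1 + added variance + 1)/2).

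**Step 3, p = 0.8 in full.**
- Model A: shift 0.8 × 0.6 = 0.48; added variance 4 × 0.64 × 0.16 = 0.4096; SD = √1.2048 = 1.098. Power ≈ Φ(3.536 × 0.48/1.098 − 1.96) = 33.9%. For 80% power, n = 2 × 7.849 × 1.2048 / 0.48² = 82.1, so 83 per group.
- Model B: shift 0.8 × 0.8 = 0.64; added variance 0.64 × 0.16 = 0.1024; SD = √1.0512 = 1.025. Power ≈ 59.8%. For 80% power, n = 2 × 7.849 × 1.0512 / 0.64² = 40.3, so 41 per group.

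**Step 4, the range, at 25 per group.**

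| p | Effect kept, A | Power, A | Effect kept, B | Power, B |
|---|---|---|---|---|
| 0.5 | 0% | 5% | 50% | 27% |
| 0.7 | 40% | 17% | 70% | 48% |
| 0.8 | 60% | 34% | 80% | 60% |
| 0.9 | 80% | 57% | 90% | 71% |
| 1.0 | 100% | 81% | 100% | 81% |

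Under Model B the left-side value keeps only 1 − p of the effect, which is 20% at p = 0.8.

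**Step 5, check.** Simulated t-tests (5,000 runs per setting) gave 33% (A) and 58% (B) at p = 0.8, 5% and 27% at p = 0.5, and 78% to 79% at p = 1.0. All are within about 2.5 points of the formula.

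**What is not affected.** If scoliosis reduces movement equally on both sides, the right-side mean shifts by the full amount whatever p is. Sway amounts and the four movements not named by side carry no sign that could mix.

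**The case against.** The strongest reply is that section 3.6 does not say right and left values are compared as such. They might be averaged, turned into an absolute asymmetry, or aligned to the curve, and that derivation commonly sits in an SAP, which is not shown here. Recording by body side is also the natural raw form: with the radiographs on file, the side can be read at any time before analysis, and the pattern or scoliometer entries may already carry it. This stands in part. The silence on derivation is not itself an error, and the harm is conditional on body-side values being used. But section 3.5 lists the curve variables in detail and side is not among them. A recoding rule written later needs that variable.

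A second reply is that the documents do not show that restriction in AIS is tied to the convex or concave side. The background describes deviations in the frontal and axial planes, but the functional changes it reports are not side-specific. This stands, so the point is worded as applying to any side-specific effect.

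Three stronger readings are tempting and should not be drawn:
- That asymmetries cancel. Full cancellation needs opposite shifts and a 50:50 mix of convexities; otherwise there is dilution.
- That sway is affected. Right-left sway is recorded as an amount along an axis and cannot cancel by sign.
- That H4 is undermined. H4 concerns sitting, standing and walking, none of which is named by side.

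**Conclusion.** The point holds for trunk rotation, lateral flexion and right and left stability limits, and for nothing else in the measurement set. Side of convexity is not a named data item and no alignment is described, so a comparison or correlation by body side would dilute a side-specific effect and inflate the AIS variance. The loss may be small (71% power instead of 81% if only the convex side is affected and 90% of curves share a side) or severe (34% if the sides shift oppositely and 80% share a side). It is nil if all curves share a side or if both sides are equally affected. The effect of 0.8 SD, the 25 per group and the mix of sides are all assumptions; the protocol fixes none of them. The change is cheap enough to be worth making without knowing which case applies.

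**What to change.** 1. Add side of convexity, for each curve, to the curve data form in section 3.5, read from the existing radiograph.
2. State in section 3.6 that, in the AIS group, rotation, lateral flexion and lateral stability limits are analysed as toward convexity or toward concavity of the curve with the largest Cobb angle. Show double curves separately as well, because one side does not describe them fully.
3. For controls, assign each one a side coding at random, in the same proportions as the AIS group, or compare within-person side differences between groups. Do not set the mean of a control's two sides against a single-side AIS value: with equal variances and correlation ρ between sides, that mean has (1 + ρ)/2 of the single-side variance, so the group variances would differ by construction.
4. Leave sway amount, flexion, extension, standing up and walking as they are.

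The cost is one extra form field per curve, a recode before analysis, and a convention for double curves that is a choice and should be stated as one. No new measurement is needed, and the raw right and left values are kept.
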